### **3.4. Safety Endpoints**

All safety endpoints are secondary endpoints.

- Proportion of subjects with major bleeding events during dalteparin treatment.
- Relationship between major bleeding event and the Anti-Xa level during dalteparin treatment if data permits.
- Proportion of subjects with minor bleeding events during dalteparin treatment.
- Time to first major bleeding events during dalteparin treatment.

Safety will also be assessed by adverse event reports, physical examination, laboratory test results, and vital signs in the safety population. Both all-causality and treatment related adverse events will be assessed. The latest Pfizer Data Standard (PDS) will be used for reporting.

### **3.4.1. Adverse Events**

An adverse event is considered treatment emergent if:

- the event occurs for the first time during the effective duration of treatment and was not seen prior to the start of treatment, or
- the event was seen prior to the start of treatment but increased in severity during treatment.

The effective duration of treatment is determined by the lag time (30 days). Any event occurring within the lag time, whether this occurs during a break in treatment or at the end of treatment, is attributed to the previous treatment period.

### **3.4.2. Laboratory Data**

To determine if there are any clinically significant laboratory abnormalities, the hematological and clinical biochemistry and other safety tests will be assessed against the criteria specified in the Pfizer reporting standards. This assessment will take into account whether each subject's baseline test results are within or outside the laboratory reference range for the particular laboratory parameter.

## **4. ANALYSIS SETS**

The main subject populations to be used for the analysis are a pharmacodynamics (PD) population and a safety population.

The PD population will be the analysis population for efficacy.

### **4.1. PD Analysis Set**

The PD analysis set (PD population) will include all subjects who receive at least one dose of study drug and achieve therapeutic range of anti-Xa during dose adjustment phase.

### **4.2. Safety Analysis Set**

The safety analysis set (safety population) will include all the subjects who receive at least one dose of study drug.

### **4.3. Protocol Deviations**

Protocol deviations relevant to the PD population and the safety population will be summarized.

## **5. GENERAL METHODOLOGY AND CONVENTIONS**

The final primary analysis will be performed at database release after last subject last visit.

## **5.1. Hypotheses and Decision Rules**

Because of the descriptive nature of this study, there will be no statistical hypotheses tested and decisions rules. Two-sided 95% confidence interval (CI) will be provided to aid decision making.

## **5.2. General Methods**

The following sub-sections contain the descriptions of the methods that will be used in the analysis of the various endpoints in this study. The choice of analysis method will be dependent on the endpoint of interest (eg, whether the endpoint is a primary or secondary, or whether the endpoint is efficacy or safety). The analysis methods to be used for each endpoint will be covered in the following section.

### **5.2.1. Analyses for Binary Endpoints**

Response rates (eg, proportion of subjects with objectively documented new or progressive symptomatic VTE) will be presented with exact 95% confidence intervals for binomial proportion, using the Clopper-Pearson method (Collett 1991).

### **5.2.2. Analyses for Continuous Data**

Continuous data are variables that are continuous or considered continuous for the purpose of analysis, the following descriptive statistics will be provided at each visit (including the baseline, when applicable): N, mean, median, standard deviation (SD), minimum and maximum.

### **5.2.3. Analyses for Categorical Data**

Categorical data will be presented with frequency and percentage.

### **5.2.4. Analyses for Time to Event Data**

Time-to-event endpoints will be summarized using the Kaplan-Meier method and estimated survival curves will be displayed graphically when appropriate. Kaplan-Meier graphs will describe the number of patients at risk over time. In addition, the Cox Proportional Hazard Regression model will be employed to assess the hazard ratio of the event with prognostic factors.

## **5.3. Methods to Manage Missing Data**

For efficacy endpoints, missing data will not be imputed.

## **6. ANALYSES AND SUMMARIES**

All statistical analyses will be performed using SAS® (Version 9.1 or higher), and statistical tests will be assessed at the two-sided 0.05 level of significance.

### **6.1. Endpoint(s)**

#### **6.1.1. PD Endpoints**

Unless otherwise noted, all PD endpoints will be analyzed within the PD population.

#### **6.1.1.1. Primary PD Endpoint**

- Anti -Xa activity versus time profile following dalteparin treatment in pediatric subjects of different ages with VTE (detailed in a separated population modeling analysis plan [PMAP-EQDD-A630c-DP4-560]).
- Median dose required to achieve an anti-Xa level of 0.5 to 1.0 IU/mL during the dose adjustment phase.

The median dose will be presented overall and by each age group for patients who achieved an anti-Xa level of 0.5 to 1.0 IU/mL during the dose adjustment phase.

#### **6.1.1.2. Secondary PD Endpoints**

- Proportion of subjects achieving an anti-Xa therapeutic range of 0.5 to 1.0 IU/mL during the Dose Adjustment Phase.

The count and proportion will be summarized overall and by each age group within the safety population, along with the two-sided exact 95% CI.

- Proportion of subjects who remain within therapeutic range at each visit during the follow up phase (Visit 5, Visit 6 and Visit 7).

The count and proportion will be summarized overall and by each age group, along with the two-sided exact 95% CI.

- The percentage of anti-Xa levels measured 4 hours post dose  $\pm 1$  hour that are outside the target range will be calculated at each visit during the follow up phase of study (Visit 5, Visit 6 and Visit 7).

The count and percentage will be summarized overall and by each age group, along with the two-sided exact 95% CI.

- The maintenance dose, time to achieve the target range, and number of dose adjustment during dose adjustment phase.

The maintenance dose, time to achieve the target range, and number of dose adjustments will be summarized overall and by each age group.

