However, the first Anti-Xa level may be taken after the first, second or third dose per Investigator judgment. The next dalteparin dose will be adjusted if the target therapeutic range is not achieved. If the therapeutic range is not achieved, the dalteparin dose must be adjusted per protocol. All plasma samples should be drawn within the assigned window at each visit, however, if this is not possible, record the actual time the sample is drawn). Plasma samples drawn during the Dose-Adjustment Phase and Follow-Up Phase that deviate outside the  $4 \pm 1$  hr window cannot use the anti-Xa reference range, 0.5-1.0 IU/mL, and should be repeated the next day for both central and local labs. The actual dosing time prior to the repeat plasma sample draw and the actual time of the repeat sample draw must be recorded.

After dose adjustment, Anti-Xa levels should be re-measured after the first, second or third dose per Investigator judgment. Dosage can be adjusted a maximum of up to 6 times (up to Day 7) to achieve Anti-Xa therapeutic range. If the target range is not achieved within the 7 day period, the subject is withdrawn from the study.

The dose at which a therapeutic Anti-Xa level is achieved is then maintained as the therapeutic dose in subsequent phases of the study unless dose adjustment is necessary.

- Pharmacodynamic Phase (Following completion of Dose Adjustment Phase) Day 2 or 3 up to Day 14 [up to 7 days]: Subjects completing the Dose Adjustment Phase will enter into the PD Phase and continue daily dosing every 12 hours  $\pm 1$  hour of dalteparin sodium with the final maintenance therapeutic dose from the Dose Adjustment Phase (no less than 8 hours between doses). However, if a dose is not able to be delivered every 12 hours  $\pm 1$  hour, administer the dose (no less than 8 hours between doses) and record the actual dosing time. The plasma sample should be re-drawn, if possible, at the correct time point.
- Follow-up Phase (Visits 5, 6 and 7, following completion of Pharmacodynamic Phase): Dalteparin sodium will be administered subcutaneously every 12 hours  $\pm 1$  hour (no less than 8 hours between doses) during Visits 5, 6 and 7. However, if a dose is not able to be delivered every 12 hours  $\pm 1$  hour, administer the dose (no less than 8 hours between doses) and record the actual dosing time.

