### **12.3.2. Definition of Study Populations for Analysis**

There will be two analysis populations defined in the study.

- Safety Population: Subjects who receive at least one treatment of dalteparin. All safety analysis will be based on this population;
- Pharmacodynamic Population: Subjects in the Safety Population who achieve therapeutic range of anti-Xa during Dose Adjustment Phase. This population will be the primary analysis population for PD and efficacy analysis.

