### **12.3.4. Analysis of Pharmacodynamic Variables**

All PD variables will be analyzed within the PD population.

The primary study analysis will be a PD evaluation of dalteparin based on Anti-Xa levels using a population PD analysis methodology. Due to the sparse plasma sampling strategy, population PD analyses will be explored. The PD effect (Anti-Xa level) is used as a surrogate PK of dalteparin for the time course of drug exposure. The population PD analysis may also be named as a population PK analysis. Details of the Population PD analysis will be described in a separate population PD modeling analysis plan document and results will be presented in a separate population PD report.

The secondary PD analyses will include the proportion of children achieving an Anti-Xa therapeutic range of 0.5 to 1.0 IU/mL at 4 hours  $\pm$  1 hour post-dose during the Dose Adjustment Phase (up to 7 days) and the proportion of subjects who remain within therapeutic range over the Follow-Up Phase (Visits 5, 6 and 7). These analyses will be descriptively summarized for all subjects and by age groups.

The final dose of dalteparin given to a subject during the Dose Adjustment Phase of the study will be considered the maintenance therapeutic dose (ie, the dose achieving an Anti-Xa level of 0.5 to 1.0 IU/mL at 4 hours  $\pm$  1 hour post-dose). The time to achieve the target range is defined as the number of days from the first dose to the final dose that achieves the target Anti-Xa level. The maintenance dose, time to achieve the target range, and number of dose adjustments during the Dose Adjustment Phase will be summarized by age group using summary statistics.

Aggregate PD profiles (curves of Anti-Xa level versus hours after dosing time) and summary measures will be calculated using combined data for all subjects within a given age group.

Additionally, for each age group, the percentage of Anti-Xa levels measured 4 hours post-dose  $\pm$  1 hour post-dose that are outside the target range will be calculated during the Follow-up Phase of the study.

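### Time to target and number of dose adjustments are summarised only in children who reached the anti-Xa range, which biases time to target downward and probably the adjustment count too

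*SAP*

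**What the plan says.** SAP 6.1.1.2 lists three titration summaries in one bullet: "The maintenance dose, time to achieve the target range, and number of dose adjustments will be summarized overall and by each age group". The bullet names no analysis set. SAP 6.1.1 supplies the default: "Unless otherwise noted, all PD endpoints will be analyzed within the PD population". SAP 4.1 limits that set to treated children who "achieve therapeutic range of anti-Xa during dose adjustment phase".

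The protocol agrees. Section 12.3.2 defines the PD population as "Subjects in the Safety Population who achieve therapeutic range of anti-Xa during Dose Adjustment Phase", and section 12.3.4 says "All PD variables will be analyzed within the PD population".

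One endpoint in SAP 6.1.1.2 is moved out of the default. The proportion reaching the range is "summarized overall and by each age group within the safety population".

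Protocol 12.3.4 gives the definition: "The time to achieve the target range is defined as the number of days from the first dose to the final dose" that reaches the target level. Protocol section 7 sets the limit on titration: "Dosage can be adjusted a maximum of up to 6 times (up to Day 7) to achieve Anti-Xa therapeutic range". Sections 7 and 8.2 withdraw children who are not in range by then. SAP 5.2.2 lists the descriptive statistics for continuous data as N, mean, median, SD, minimum and maximum.

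**The concern.** Time to target is an event time with a seven-day limit. A child who reaches the limit without the event has not lost the observation: it is known that the time exceeds seven days. The plan removes that child from the summary.

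No other rule brings these children back. The censoring rule in SAP Appendix 1.1 is invoked only for recurrent VTE and major bleeding, and the missing-data rule in SAP 5.3 covers efficacy endpoints only. Under protocol 6.3.2, children who do not complete the PD Phase are replaced until 50 have viable data. Failures therefore add to the number treated and never enter these two summaries.

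At stake is how a reader judges the starting doses. Protocol 5.1 states the aim as dosing recommendations by age, and these endpoints say how long titration takes and how many steps it needs. If the failure share differs by age group, so does the bias, and the comparison between age groups is distorted.

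**Working it through.** **1. The plan's own figure.** Daily checks on Days 1 to 7 leave 7 − 1 = 6 intervals for a dose change, which matches the stated maximum of six. Protocol section 7 also allows the check after a change to wait for the third dose. Seven days of twice-daily dosing is 14 doses, so checking only after every third dose gives 4 checks and about 3 to 4 adjustments. Both six and three are used below.

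**2. Direction for time.** Every achiever's time lies within the seven days, and every child still out of range at Day 7 has a time beyond it. Dropping such children can only lower the mean, and can only lower the median or leave it unchanged.

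**3. Possible size for time.** The documents give no failure share f, so 5% to 40% is assumed. Take a constant daily chance q of reaching the range, with f = (1 − q)^7, and set failures at Day 7, which is a lower bound. With m the mean in achievers, the all-treated mean is (1 − f)·m + 7f, so the gap is f·(7 − m). For f = 10%: q = 1 − 0.10^(1/7) = 0.280, m = 2.79, and 0.9 × 2.79 + 0.7 = 3.21. For medians, failures count as later than Day 7.

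| f (assumed) | Mean day: achievers vs all | Median day: achievers vs all |
|---|---|---|
| 5% | 2.50 vs 2.73 | 2 vs 2 |
| 10% | 2.79 vs 3.21 | 2 vs 3 |
| 20% | 3.12 vs 3.89 | 3 vs 4 |
| 30% | 3.33 vs 4.43 | 3 vs 5 |
| 40% | 3.48 vs 4.89 | 3 vs 6 |

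Counting the first day as zero shifts both columns equally and leaves the gaps unchanged.

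**4. Possible size for adjustments.** Assumed: start 125 IU/kg, lognormal first level with CV 50%, level proportional to dose, 25 IU/kg steps, and every child followed to the limit. On the log scale the SD is √ln(1.25) = 0.472. With six steps up the dose reaches 275 IU/kg, 2.2 times the start, so a child fails if the first level is below 0.5/2.2 = 0.227 IU/mL. At a median of 0.45 that is Φ(−ln(0.45/0.227)/0.472), about 7%. With three steps the factor is 1.6 and the cut-off 0.3125, giving about 22%. The few children who stay too high add very little. Means come from simulation.

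| Median first level (IU/mL) | Six possible: achievers vs all | Three possible: achievers vs all |
|---|---|---|
| 0.45 | 1.55 vs 1.88 | 0.95 vs 1.40 |
| 0.55 | 1.12 vs 1.27 | 0.77 vs 1.03 |
| 0.70 | 0.86 vs 0.91 | 0.71 vs 0.82 |

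Check of the first cell: 0.926 × 1.55 + 0.074 × 6 = 1.88.

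**5. Reversal between groups.** In the same model, take a median first level of 0.35 and six adjustments. A group with CV 30% (7% failures) shows 2.59 in achievers and 2.83 in all. A group with CV 70% (25% failures) shows 2.01 and 3.00. The second group looks easier to titrate among achievers and is harder overall.

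**6. Why the count is less certain than the time.** Suppose achievers average 1 adjustment and 20% of treated children leave early with none. The all-treated mean is then 0.8 × 1 + 0.2 × 0 = 0.8, below the achiever mean.

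**The case against.** The strongest case is that failures are not hidden. The proportion reaching the range is reported in the Safety Population, overall and by age group, with exact intervals, in the same SAP section. Time to target is also defined only for a child who reaches it, so an achiever summary is a legitimate conditional description. Both points stand, but they do not settle the matter. A failure count says nothing of how long those children were titrated or through how many steps. The listed statistics also do not give the daily distribution that a reader would need to combine with the failure share.

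Protocol 12.3.6 lists the number of dose changes per child among the safety summaries. This is a partial remedy for the count only. It covers the whole study rather than the Dose Adjustment Phase, and SAP 6.2.3 specifies only treatment duration.

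The gap may also be small. Protocol 8.4 says that similar dosing gave levels within the target range. With a median first level of 0.70 IU/mL and six adjustments, the difference is only 0.05. With about 10 children per age group and an SD near 2.0, the standard error of a mean count is about 2.0/√10 = 0.63, larger than the 0.33 gap at 0.45 IU/mL. This stands as a limit on importance, although imprecision does not remove a bias of known direction.

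A reader might go further and infer that reported results are inflated by one over the success share, for example by 25% with 20% failures. That factor applies to a percentage in range by a given day, which the plan does not report, and not to a mean or median. A reader might also infer that the children with the most adjustments are always the ones dropped. Early exits and checks after the third dose mean that the documents do not support this.

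**Conclusion.** The restriction follows from both documents. The downward bias in time to target is certain in direction whenever any treated child is still out of range at Day 7. The bias in the adjustment count is probable but not certain.

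The size cannot be fixed from the documents. Under the assumed failure shares of 5% to 40%, mean time is understated by about 0.2 to 1.4 days and median time by 0 to 3 days. In the titration model, mean adjustments are understated by 0.05 to 0.33 with six possible and by 0.11 to 0.45 with three. These figures rest on the assumed first level, the spread, dose proportionality and no early exits. Reversal between age groups is possible, but it depends on unequal failure shares and is not predicted here.

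The endpoints are secondary and descriptive, and SAP 5.1 plans no hypothesis test. The two primary PD analyses do not depend on these summaries. The point is a worthwhile, inexpensive correction of modest priority.

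**What to change.** In SAP 6.1.1.2:

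- Report time to target in the Safety Population as the cumulative proportion in range by each day to Day 7, overall and by age group, with exact 95% CIs. Count children not in range at Day 7 as not in range. Keep children who leave before then in the denominator and show them as a separate category.
- Report the number of adjustments during the Dose Adjustment Phase for all treated children, split into achieved, not achieved by Day 7, and left early.
- Keep the maintenance dose in achievers, since it exists only there, and label any achiever-only summary as conditional on reaching the range.

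Confirm before database release that titration data are complete for non-achievers. Protocol 9.3.2 says the dose-adjustment CRF pages are completed once the optimal dose is reached, whereas protocol 6.3.1.1 requires all observations up to termination to be recorded. Protocol 5.2 and 9.1.8 already require actual dosing and sampling times on the CRF, so no new assessment is needed.

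The cost is SAP wording, one more table shell and that data check. The downside is that the reported figures become slightly less favourable.

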#### **6.1.2. Efficacy Endpoints**

All efficacy endpoints will be analyzed within the PD population.

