In the Follow-Up Phase, subjects will continue daily dosing every 12 hours  $\pm$ 1 hour with dalteparin sodium with the final dose from the Dose Adjustment Phase (no less than 8 hours between doses) until EOS or ET. However, if a dose is not able to be delivered every 12 hours  $\pm$ 1 hour, administer the dose (no less than 8 hours between doses) and record the actual dosing time. In-clinic visits will occur on Visits 5, 6 and 7 for safety, and efficacy assessments, and Anti-Xa plasma samples. Dose adjustments can be made during these visits if necessary. The Principal Investigator or designee will follow-up weekly during a telephone interview with subjects and/or caregivers after discharge from the hospital to assess study compliance and general well-being. Subjects will have repeat imaging (using the same imaging method used at Screening) at the EOS visit or Early Termination (ET) visit to measure clot resolution.

For non-cancer patients who stop dalteparin treatment prior to 3 months according to the ACCP Guidelines, Anti-Xa and Anti-IIa plasma sampling will not be required after study medication discontinuation.

Treatment will continue until any of the following occurs:

- New or progressive VTE (whether symptomatic or asymptomatic);
- Bleeding necessitating permanent discontinuation of anticoagulant therapy;
- Unexpected thrombocytopenia;
- Other AEs necessitating discontinuation of study drug, withdrawal of consent, or scheduled study termination completion;
- Unexpected permanent discontinuation of anticoagulation therapy.

For procedures that require interruption of study treatment, it is recommended to follow the ACCP guidelines. The guidelines state that it may be advisable to omit two doses of LMWH before procedures being performed and resume 12 to 24 hours after the procedures.

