### **12.3.5. Analysis of Efficacy Variables**

All efficacy variables will be analyzed within the PD population.

Efficacy variables include:

- Proportion of subjects with objectively documented new or progressive symptomatic VTE will be summarized overall and by age groups during dalteparin treatment; the proportions will be accompanied by an exact 95% confidence interval;
- Proportions of subjects with progression, regression, resolution, or no change in the qualifying VTE will be summarized overall and by age groups during dalteparin treatment; the proportions will be accompanied by an exact 95% confidence interval;
- Time to first episode of recurrent VTE will be analyzed using Cox regression model to assess recurrent VTE during dalteparin treatment, with prognostic factors (eg, age group, baseline tumor type). Kaplan Meier estimates of time will also be produced.

Exploratory analyses:

- Logistic regression model assessing if subjects achieve an Anti-Xa therapeutic range during the Dose Adjustment Phase, using the Odds Ratio of prognostic factors of age, gender, chemotherapy status, and dose of dalteparin.

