## **9. APPENDICES**

### **Appendix 1. STATISTICAL METHODOLOGY DETAILS**

#### **Appendix 1.1. Time to Event**

For this analysis, time to event will be measured from the first dose of study medication in days. For subjects who have event, time to event is defined as:

$$T = \text{date of event} - \text{first treatment date} + 1$$

Subjects who do not have the event of interest will be censored at the latest date in the database. Time to event is defined as:

$$T = \text{latest date in the database} - \text{first treatment date} + 1$$

The latest date is expected to be the date of the End of Study visit.

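### VTE endpoints are analysed only in children who reached the anti-Xa range, so a clot before that point is left out of them, while the clock still counts the days before it

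*SAP*

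**What the plan says.** SAP 6.1.2: "All efficacy endpoints will be analyzed within the PD population". Protocol 12.3.5 says the same: "All efficacy variables will be analyzed within the PD population".

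SAP 4.1 defines that population as "all subjects who receive at least one dose of study drug and achieve therapeutic range of anti-Xa during dose adjustment phase". Protocol 12.3.2 agrees: "Subjects in the Safety Population who achieve therapeutic range of anti-Xa during Dose Adjustment Phase".

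Protocol 7 and 8.2 each list the events at which treatment stops. The first entry in both is "New or progressive VTE (whether symptomatic or asymptomatic"). The list in Section 7 is not tied to a phase, and Protocol 5.3 also names new or recurrent VTE as a reason for early discontinuation. On children who do not reach the range, Protocol 7 says: "If the target range is not achieved within the 7 day period, the subject is withdrawn from the study".

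The VTE endpoints in SAP 6.1.2.1 cover the whole period of dalteparin treatment, which begins with the first dose. Under SAP Appendix 1.1, "time to event will be measured from the first dose of study medication in days", and children without an event are censored at the latest date in the database, expected to be the End of Study visit. Neither document plans a VTE proportion or a time-to-VTE analysis in all dosed children.

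**The concern.** Membership of the efficacy set is decided after dosing starts, by something a VTE can prevent. A child whose clot extends before the range is reached stops drug and leaves both numerator and denominator. A child withdrawn at Day 7 without reaching the range is also left out. The endpoint covers treatment from the first dose; the analysis set covers treatment that got as far as a successful titration.

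The time-to-event analysis has a linked problem. Every child in the set was still on treatment, and so under the stopping rule still free of a new or progressive VTE, when the range was reached. Those days enter the risk set although no event could be recorded in them.

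The plan handles neighbouring endpoints differently. SAP 6.1.1.2 takes the proportion reaching the range in the safety population, and SAP 6.3 does the same for bleeding. Bleeding and VTE would thus be reported on different denominators, with titration-phase events counted for one and not for the other. Replacement until 50 children have viable PD data (Protocol 6.3.2) refills the PD count but does not bring an excluded event back.

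**Working it through.** **No plan figure to reproduce.** The target of 50 comes from population-model simulation of clearance and volume (Protocol 12.1, Appendix 3). The model parameters are not given, and this point does not depend on that figure.

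**Step 1: which children are lost.**
- Symptomatic VTE before the range is reached: treatment stops, the range is not reached on study drug, the child is outside the set, and the event is not counted.
- Range not reached by Day 7: withdrawn, outside the set.
- VTE after the range is reached, even within the first week: inside the set, and the event is counted.

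**Step 2: event-free time by construction.** Share = days from first dose to range ÷ days on the clock. End of study is Day 90 ± 14 (Protocol 5.3).
- 1 day: 1/90 = 1.1%
- 3 days: 3/90 = 3.3%
- 7 days (the ceiling): 7/90 = 7.8%; across the window, 7/104 = 6.7% to 7/76 = 9.2%

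Short titrations are plausible. The first sample may follow the first, second or third dose, an adjustment can be made on Day 1 (Protocol 9.3), and the PD Phase can open on Day 2 or 3 (Protocol Table 1).

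**Step 3: effect on the proportion.** The counts are assumed. Intervals are Clopper-Pearson, as in SAP 5.2.1.

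| Planned (PD set) | Excluded children | All dosed |
|---|---|---|
| 2/50 = 4.0% (0.5 to 13.7) | 1, with 1 event | 3/51 = 5.9% (1.2 to 16.2) |
| 2/50 = 4.0% (0.5 to 13.7) | 2, with 2 events | 4/52 = 7.7% (2.1 to 18.5) |
| 0/50 = 0% (0 to 7.1) | 1, with 1 event | 1/51 = 2.0% (0.05 to 10.4) |
| 2/50 = 4.0% (0.5 to 13.7) | 10, with 0 events | 2/60 = 3.3% (0.4 to 11.5) |

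**Step 4: expected size under a simple hazard model.** Assume a VTE hazard m times higher in days 1 to 7 than in days 8 to 90, and an average of d days to the range. For a low event rate, the share of 90-day risk that falls before the range is about m·d ÷ (7m + 83).
- m = 1: d = 2 gives 2/90 = 2.2%; d = 4 gives 4/90 = 4.4%
- m = 3: 6/104 = 5.8%; 12/104 = 11.5%
- m = 5: 10/118 = 8.5%; 20/118 = 16.9%

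A simulation of 2,000,000 children per scenario agrees. It assumed a 90-day risk of 3%, 6% or 10%, days to range uniform over 1-3 or 1-7, and 10% never reaching the range, independently of VTE risk. The PD-set proportion was too low, in relative terms, by about 2% and 4-5% (m = 1), 6% and 11% (m = 3), and 8-9% and 16-17% (m = 5). The comparison is with the 90-day risk in all children followed to Day 90, not with a crude all-dosed proportion in which non-achievers leave by Day 7.

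**The case against.** **The endpoints are secondary.** VTE is to be explored, there is no control group, and SAP 5.1 sets no hypothesis or decision rule. The primary PD endpoints are untouched. This stands, and it lowers the priority.

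**The event is not hidden.** A VTE in an excluded child, recorded as an adverse event, appears in the safety-population tables (SAP 6.3.2), and withdrawal reasons and set sizes are reported (SAP 6.2.2). This also stands. A reader might infer that such events vanish from the report; they do not. They are missing from the VTE analyses.

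**The direction is not certain.** A reader might infer that the planned proportion must favour the drug. The documents do not show that. Non-achievers add to the denominator with little follow-up, so if none has an event the all-dosed crude proportion is lower (2/60 against 2/50). The larger relative errors in Step 4 need a raised early hazard, which the documents do not give, and the intervals in Step 3 overlap heavily.

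**The event-free share is small.** A reader might set 7 days against a 6-week course, 7/42 = 16.7%. The text does not support this. The clock runs to the End of Study visit, non-cancer children stay for the full 3 months, and the 6 weeks are stated as following the PD Phase (Protocol 5.1). Even on treatment time the denominator would be 7 + 1 to 7 + 42 = 50 to 56 days, giving 12.5 to 14%. Seven days is itself a ceiling.

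**Not every VTE analysis can move to all dosed children.** Images from children withdrawn by Day 7 are not comparable with Day 90 images. The logistic model in SAP 6.1.2.1 needs anti-Xa at the end of dose adjustment, which may not exist, or may follow the event, in a child who clotted during titration. Both points stand and limit the fix.

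None of this supplies a reason for confining the VTE proportion and the time-to-event analysis to achievers, and the documents state none.

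**Conclusion.** The point holds. Read together, the definition of the set, the stopping rule and the time origin leave any VTE before the range is reached out of the VTE proportion, its interval, and the Kaplan-Meier and Cox analyses. They also count up to 7 days per child as time at risk in which no event could be recorded. This follows from the text and needs no assumption about rates.

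The size does need assumptions. The event-free share is about 1 to 3% of a 90-day clock for titrations of 1 to 3 days and at most 7.8% at 7 days. With few events, a single excluded one matters: 4.0% becomes 5.9%, or an apparent zero becomes 2.0%. If there are no excluded events, the crude proportion hardly changes or falls slightly. This should be corrected before analysis, but it does not threaten the primary objectives.

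**What to change.** In SAP 4 and 6.1.2 and Protocol 12.3.2 and 12.3.5:

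1. Make the safety population the main set for the proportion with new or progressive symptomatic VTE and for time to first recurrent VTE. Start the clock at first dose, count events in the Dose Adjustment Phase, and censor non-achievers at their last VTE assessment, in line with Protocol 12.3.7.
2. Keep the PD population as a supportive analysis, with its clock, or delayed entry, starting on the date the range was reached.
3. List every VTE that falls outside the PD population.
4. For change in the qualifying VTE, keep the PD population result and add an all-dosed table with early-withdrawal images and no follow-up image as separate categories. Protocol 6.3.1.1 already asks for the Visit 7 assessments at removal where possible, and these include imaging (Protocol 9.3.5).
5. Leave the logistic model on anti-Xa at the end of dose adjustment in the PD population.

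The cost is wording and one further set of tables from data already planned; no visit or procedure changes. The downsides are that the VTE proportion may look slightly worse, non-achievers contribute short follow-up, and their censoring may be informative, which the report should say.
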